5.4.9 Blinding

Part 1 and Part 2 of the study is a double-blind study and thus the Investigator, site staff and patients are all blinded to treatment. No individual-patient information that can potentially un-blind the Investigator or patient will be reported until the end of the study. The presentation of the placebo will be identical in appearance to the study drug.

A communication plan will describe the procedure for un-blinding the study. The Investigator at the site will have access to the details of the double-blind treatment for each patient. Access to these details will be via RTSM.

Note!: The Investigator may only break the code **if knowledge of the study medication is necessary to provide optimal treatment to the patient in an emergency situation.** Whenever possible, the Investigator must consult with the sponsor before breaking the code. The unblinding procedure is described in RTSM User Guide.

Emergency unblinding will not preclude patient's data being included in the study analyses. The primary efficacy analyses are performed on an intention-to-treat basis (Section 8.3.2, Section 8.3.3), and unblinding will not result in a patient being excluded from any analysis sets. Similarly, safety will be assessed using the safety population (Section 8.3.1), which includes all patients who received at least one dose of study drug, regardless of any subsequent unblinding. However, a listing of all cases requiring unblinding will be provided, including details of the reason for unblinding.

Unblinding of all study treatment assignment will be performed at the time of data cut-off (DCO) of Part 1 and Part 2 of the study respectively before primary analysis.

The data cut-off for the primary analysis of Part 1 will be the later of 3 months after Last Patient In (LPI) or when 70% of the patients (84 patients) have experienced PFS events, while the data cut-off for Part 2 will be when 247 OS events have occurred.

After the treatment allocation is unblinded post DCO, all patients receiving active treatment and who, in the opinion of the investigator, may benefit from continued varlitinib treatment, will be offered participation in an open-label extension study where only varlitinib will be provided by the sponsor; or be managed under a compassionate use program governed by the regulatory authorities in the respective countries.

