8.2.2 Part 1 Sample Size

Part 1 is designed with co-primary endpoints ORR and PFS. In order to maintain an overall, 1-sided 10% type I error rate for Part 1, a Hochberg procedure¹⁵ will be used, such that the study will be deemed to have met its primary objective if either endpoint is significant at the 1-sided 5% level or if both endpoints are significant at the 1-sided 10% significance level.

One hundred and twenty patients provide approximately 80% power to detect a true difference of 17% in response rate, based on a 1-sided 5% significance level and assuming 10% response rate for the placebo group and a 27% response rate for varlitinib. To ensure the adequate data are available to evaluate the effects of varlitinib on both co-primary endpoints, the DCO for the primary analysis will be the later of 3 months after last patient in and when 70% of patients (84 patients) have experienced a PFS event. Based on a minimum of 84 PFS events at the time of the primary analysis, the study would have a minimum of 80% power to detect a true HR of 0.58 for PFS based on a 1-sided 5% significance level.

Furthermore, if the primary objective of the study is met, the following approach to type I error control will be applied in order to support marketing approval:

- The overall type I error rate for marketing approval will be controlled at the two-sided 5% level, using a Hochberg procedure
- Using this approach, statistical significance may be claimed if *either* ORR or PFS is significant at the two-sided 2.5% significance level or if *both* ORR and PFS are significant at the two-sided 5% significance level.

One hundred and twenty patients provide approximately 80% power to detect a true difference of 20% in response rate, based on a 2-sided 5% significance level and assuming 10% response rate for the placebo group and a 30% response rate for varlitinib.

A total of 84 PFS events provides 80% power to detect a true HR of 0.54, based on a two-sided 5% significance level. Assuming a 8-month non-linear recruitment period, a 2.67 month median PFS for capecitabine alone, and a true HR of 0.54, it is estimated that the DCO for the primary analysis of Part 1 will occur approximately 12 months after the first patient is randomized into the study (first patient in).

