8.4.3 Overall Survival

Overall survival is a secondary endpoint in Part 1, and the primary endpoint in Part 2 of the study.

Overall survival is defined as the time from the date of randomization until death due to any cause. Any patient not known to have died at the time of DCO will be censored based on the last recorded date on which the patient was known to be alive.

Note, survival calls may be made in the week following the date of DCO for the analysis, and if patients are confirmed to be alive or if the death date is after the DCO these patients will be censored at the date of DCO.

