### 4.4 Per Protocol Analysis Population

The per-protocol analysis population is defined for Part 1 only. Efficacy is not the focus of the Safety lead-in and Part 2 will be assessed on an intention to treat basis only. Thus PP analyses are not required for the Safety lead-in and Part 2 of the study.

The per-protocol analysis population will include all randomized subjects according to the treatment actually received, and excluding any subjects with major deviations. Major deviations that would lead to exclusion from the per-protocol analysis population include:

- Subjects who did not have the intended disease (failure of inclusion criteria 2)
- Subjects who did not have the intended indication, i.e. were not second line patients (failure of inclusion criteria 3)
- Subjects who did not received any randomized therapy
- Subjects with baseline radiological scan performed before the start of protocol-specified interval prior to randomization
- Subjects who did not have measurable disease at baseline as determined by ICR
- Subjects who have not received at least six doses of gemcitabine in a first line setting (i.e. failure of inclusion criteria 4, protocol version 4.0 onwards)
- Subjects with multiple ( $\geq 2$ ) peritoneal metastases at baseline or ascites at baseline which cannot be attributed to a non-malignant cause (i.e. failure of exclusion criteria 3, protocol version 3.0 onwards), based on ICR review
- Subjects with baseline albumin  $< 3$  g/dL (failure of the albumin component of inclusion criteria 9c)

In addition to the programmatic determination of the major deviations, monitoring notes or summaries will be reviewed to determine any important post entry deviations that are not identifiable via programming, and to check that those identified via programming are correctly classified. The final classification will be made blinded, prior to database lock. For example, details of disallowed concomitant medication use will be reviewed by a physician, blinded to treatment allocation, and may be deemed major.

Subjects who received the incorrect randomized therapy should be included in the PP analysis set according to the therapy actually received. Similarly, subjects who were mis-stratified at randomization will be included in the PP analyses according to the correct stratification levels, regardless of the levels declared at randomization.

Note, failure of an inclusion/exclusion criteria will not automatically be classified as a major deviation.

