## 6.7 Stratification Factors

As described in Section 2.2, for Parts 1 and 2, the randomization scheme will be stratified by region (US/Non-US) and primary tumor location (GB/Non-GB). It is planned that all formal statistical analyses will be stratified by the same two factors, using the values declared at randomization.

In the event that any individual stratum is very small, and contains limited information (i.e. events or responders), certain stratified analysis techniques may result in the entire stratum's data being "omitted" from the fitted model. Furthermore, even when the primary analysis can be fitted, if the information within the stratum is limited, the treatment by stratum interaction tests are unlikely to be meaningful, and the planned sub-group analyses may also become problematic.

If there are fewer than 8 patients in any of the 4 strata, the number of events (PFS and OS) and responders (ORR and DCR) within the affected stratum will be reviewed, prior to study unblinding. If at the blind review stage there is deemed to be insufficient information within the stratum to make the planned stratified analysis meaningful, geographical region will be "dropped" as a stratification factor from the statistical analyses, and the primary analyses would remain stratified by primary tumor location (GB/non-GB). The reason for removing geographical region rather than primary tumor

location as a stratification factor, is that it is anticipated that the percentage of GB:non-GB patients will be closer to 50:50, therefore geographical region is the stratification factor most likely to be driving the small stratum.

In this scenario, geographical location (US/non-US) would be added to the list of factors to be explored as part of the planned sub-group analyses. As noted above, any decision to exclude geographical region as a stratification factor in the analysis would be made prior to study unblinding, and would be fully documented in the study file.

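### Treatment codes are released at data cut-off, ahead of the permitted post-cut-off survival calls and with no stated order relative to database lock and the required blinded reviews

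*Protocol*

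**What the plan says.** Protocol 5.4.9 sets the rule: "Unblinding of all study treatment assignment will be performed at the time of data cut-off (DCO) of Part 1 and Part 2", continuing "of the study respectively before primary analysis". That last phrase is the only order given. The section defines the Part 1 cut-off as "the later of 3 months after Last Patient In (LPI) or when 70% of the patients (84 patients) have experienced PFS events" and states that the "data cut-off for Part 2 will be when 247 OS events have occurred". It leaves the unblinding procedure to a communication plan that is not among the documents supplied.

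Other sections describe work that follows cut-off or must be done blinded:

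- **Survival status.** Protocol 8.4.3 says "survival calls may be made in the week following the date of DCO for the analysis", and patients then found alive, or to have died after cut-off, are censored at the cut-off date. SAP 3.1.3 repeats this. The Protocol synopsis and Section 6.2.5 say the same for Part 1.
- **Deviation and per-protocol classification.** SAP 4.4: "The final classification will be made blinded, prior to database lock". Protocol 8.3.4 has the same requirement, and SAP 5.1 applies it to Parts 1 and 2.
- **Stratification.** SAP 6.7: "any decision to exclude geographical region as a stratification factor in the analysis would be made prior to study unblinding".
- **Tumor size.** The choice to log-transform is made at a blind review (Protocol 8.5.2.1, SAP 7.6).
- **PK set.** Its membership is settled before unblinding (SAP 4.5 and the Protocol synopsis).

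On lock, SAP 6 places it at the Part 1 primary-analysis point, and SAP 6.4.2 places it at the Part 2 data cut-off.

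**The concern.** Cut-off is a date fixed by an event count or elapsed time. Data up to that date still have to be collected, and some judgements about them still have to be made. A rule that releases every code on that date puts those tasks on the wrong side of the blind.

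The task that matters most is survival ascertainment in Part 2. A patient who is reached contributes either a death or follow-up to cut-off; a patient who is not reached is censored at the last date known alive. If allocation is known when the calls are made, the effort spent on each patient can differ by arm, and so can the censoring pattern. Protocol 5.4.9 also offers the extension to patients on active treatment once allocation is unblinded, which suggests that sites, who make the calls, would learn it.

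The second task is the final deviation classification, where the review of monitoring notes involves judgement.

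**Working it through.** **1. The cut-off triggers.** Part 1: 0.70 × 120 = 84 PFS events. The power statements behind the triggers were checked with the Schoenfeld formula for 1:1 allocation, d = 4(z_α + z_β)² / (ln HR)², at 80% power:

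- HR 0.54, two-sided 5%: 4 × (1.960 + 0.842)² / (ln 0.54)² = 31.40 / 0.3797 = 82.7, so 83 events; 84 events give 80.6% power. This reproduces "A total of 84 PFS events provides 80% power to detect a true HR of 0.54".
- HR 0.58, one-sided 5%: 4 × (1.645 + 0.842)² / (ln 0.58)² = 24.73 / 0.2967 = 83.3, so 84 events; power 80.3%.
- HR 0.70, two-sided 5% (Part 2): 31.40 / 0.1272 = 246.8, so 247 events; power 80.0%.

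The triggers are sound, and none of these figures depends on when the codes are released.

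**2. Patients still open at cut-off.** If cut-off falls exactly on the event count:

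- Part 2: 350 − 247 = 103 patients not known to have died.
- Part 1: 120 − 84 = 36 patients without a PFS event. The documents give no count of patients alive at that point.

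Routine survival contact after progression is every 12 weeks (Protocol 6.3.5), so a patient's last contact can lie about 12 weeks before cut-off. The calls close that gap.

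**3. Does the order follow from the text?** A lock on the cut-off date cannot contain answers collected in the following week. So either lock comes after cut-off, or the calls are not in the locked data. Protocol 5.4.9 ties code release to cut-off, not to lock. Read literally, release precedes the calls. Whether it precedes lock is not stated anywhere.

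**4. The blinded steps side by side.**

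| Step | Requirement | What it affects |
|---|---|---|
| Survival calls | Allowed in the week after cut-off; blinding not stated | OS: Part 2 primary, Part 1 secondary |
| Deviation / per-protocol classification | Blinded, before lock | Part 1 sensitivity analyses; deviation summaries in both Parts |
| Dropping region as a stratum | Before unblinding (SAP only) | Stratified tests as the SAP has them |
| Tumor-size transformation | Blind review | A Part 1 endpoint that supports no claims |
| PK set | Before unblinding | PK analyses |

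The classification row conflicts with 5.4.9 inside the Protocol itself (5.4.9 against 8.3.4). Post-entry deviations can occur up to cut-off, so a final blinded classification cannot be complete on that day.

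**The case against.** The strongest reply is that 5.4.9 is loosely worded rather than wrong. Its closing paragraph places unblinding after cut-off, the SAP puts lock at the same milestone, and the communication plan may set the order. If the phrase means the cut-off milestone rather than the calendar day, everything can be followed. That reading is possible, but the text does not state it, and an unseen plan would not remove the conflict with Protocol 8.3.4.

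Several stronger readings are tempting, and the documents do not support them:

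- **That the analysis decisions would be made unblinded and before lock.** Both documents require the deviation classification to be blinded, and the SAP requires the stratification decision before unblinding. No section places unblinding before lock.
- **That several steps threaten both co-primary endpoints.** The primary analyses use the full analysis set. The per-protocol set is a Part 1 sensitivity set, and most of its listed exclusions are baseline facts. Tumor size is not a key secondary endpoint. OS at the Part 1 cut-off is exploratory (Protocol 8.2.2).
- **That the stratification choice is exposed.** Protocol 8.5.1.1 and 8.5.1.2 already stratify by tumor location alone. Under the SAP the trigger is fewer than 8 patients in a stratum, and stratum sizes are known once the last patient is in. The mismatch between the documents on strata is a separate matter.
- **That central reads and data queries lose their blind.** Central review is described as blinded (Protocol 7.1.2.1). Neither document sets a rule that queries be closed blinded; that is good practice, not a contradiction.

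Protocol 8.3.5 also masks subject IDs for late PK-set decisions. No such safeguard is described for the survival calls or the deviation classification.

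**Conclusion.** The point holds as a contradiction between sections and an unstated order, not as a plan to make decisions unblinded. Its main weight is on Part 2 OS: up to 103 of 350 patients could have survival status confirmed after the codes are out. That count assumes cut-off falls exactly at 247 deaths. It is an upper figure, because some of these patients will already have a recent contact or be unreachable. The documents give no basis for putting a number on the resulting bias.

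The per-protocol, tumor-size and PK steps are conflicts of lower consequence. The strata step matters only while the SAP keeps region in the analysis. No alpha, power or sample size changes.

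One limit remains under any wording: the Part 1 OS update at about 95 deaths comes after the Part 1 codes have been released for the ORR and PFS analysis.

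**What to change.** Amend Protocol 5.4.9 so that treatment codes for each Part are released only after three things have happened: survival status as of cut-off has been updated, the required blinded reviews and classifications have been documented, and the database for that analysis has been locked. State the same sequence in SAP 6 and 6.4.2, making clear that lock follows the survival calls, and align the communication plan with it.

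Protocol 5.4.5 keys the extension offer to the Part 1 cut-off, and 5.4.9 keys it to unblinding after cut-off. These passages must be reconciled with each other and with the new sequence; how is for the sponsor to decide.

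The cost is a short amendment and later unblinding, by the interval between cut-off and lock.

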5.4.10 Prior and Concomitant Therapy

Concomitant medication may be given as medically indicated. All patients will be asked to provide a complete list of concomitant medication including prescription, over-the-counter, complementary, and alternative medications that have been taken within 4 weeks before the first treatment visit. They must also inform the Investigator about any new medication started while on the study.

Details (including indication, doses, frequency, and start/stop dates) of concomitant medication taken, as well as concomitant therapy (including indication, start and stop dates) administered within 4 weeks before the first treatment visit, during the study, until the completion of the safety follow-up visit, must be documented in the medical record and the appropriate CRF.

Varlitinib

Varlitinib may cause a drug-drug interaction with other medications that are cytochrome P450 (CYP) 3A4, CYP2C8, CYP2C9 or CYP2C19 inducers, inhibitors, or substrates. Human CYP3A4 is the major route of metabolism of varlitinib, whereas CYP2C8 and CYP2C19 are minor routes. Due to the potential for drug interactions based on in vitro screens, concomitant use of moderate CYP3A4, CYP2C8, CYP2C9, and P-gp inducers or inhibitors will be recorded during the entire clinical study. Refer to the FDA's Drug Development and Drug Interactions: Table of Substrates, Inhibitors and Inducers.¹⁴

Examples of CYP2C8 substrates are:

- amodiaquine (antimalarial, anti-inflammatory)
- serivastatin (statin)
- paclitaxel (chemotherapeutic)
- repaglinide (antidiabetic)
- torasemide (loop diuretic)
- sorafenib (tyrosine kinase inhibitor)
- rosiglitazone (antidiabetic) - converted to active metabolites

Examples of strong CYP2C8 inhibitors (one that causes a > 5-fold increase in the plasma area under the plasma concentration-time curve (AUC) values or more than 80% decrease in clearance) are:

- gemfibrozil (hypolipidemic)

Examples of moderate CYP2C8 inhibitors (one that causes a > 2-fold increase in the plasma AUC values or 50% to 80% decrease in clearance):

- trimethoprim (antibiotic)

Examples of CYP2C8 inhibitors with unspecified potency:

- thiazolidinediones (antidiabetic)
- montelukast (leukotriene receptor antagonist)
- quercetin (anti-inflammatory) Examples of CYP2C8 inducer:
- rifampicin (antibiotic)

Varlitinib is a weak inhibitor of CYP2C8 and CYP2C9 with an IC₅₀ of 3.2 µM and 10.6 µM, respectively. Its plasma protein binding is higher than 99% so the free fraction of varlitinib in the blood is not likely to reach that concentration.

In the Safety Lead-in and Part 1 of the study, non-excluded drugs that are associated with torsade de pointes and QTc prolongation ([Appendix 14.4](#)) or QT Prolongation without torsade de pointes ([Drugs that Prolong Appendix 14.5](#)) should be at steady-state dosing for at least 2 weeks before enrollment. During the study, from 2 weeks before the first dose to up to and including Cycle 2 Day 1, the dose of such drugs should not be increased, and new drugs in either group should not be initiated without approval from medical monitor.

In addition to the above, in the Safety lead-in and Part 1 of the study, from Cycle 2 Day 2 onwards, the dose of drugs associated with torsade de pointes and QTc prolongation ([Appendix 14.4](#)) or QT prolongation without torsade de pointes ([Appendix 14.5](#)) ideally should not be increased. Every attempt should be made to minimize the initiation of such drugs ([Appendix 14.4](#) or [Appendix 14.5](#)). The initiation of any such drugs ([Appendix 14.4](#) or [Appendix 14.5](#)) requires the medical monitor's approval.

Capecitabine

Refer also to the XELODA[®] (capecitabine) prescribing information leaflet¹² for details of drug interactions with capecitabine.

5.4.10.1 Prohibited Medication/Therapy

Prohibited medications during this study will include

- any other antitumor treatment
- proton pump inhibitors
- warfarin
- strong CYP3A4 inhibitors
- any other investigational product
- herbal preparations
- H2 blocker can be given 3 hours after each dose of varlitinib.

Please see [Appendix 14.3 Prohibited Concomitant Medication/T](#) for the list of prohibited medication/therapy.

5.4.11 Treatment Compliance

The administration of all study medications should be recorded in the appropriate sections of the CRF. Patients shall report any self-administered medication.

Patients will be issued with a diary card, which is to be returned to the study center at the next visit. Treatment compliance of self-administered study medication will be assessed by regular tablet counts on the patient diary card and the information will be recorded in the appropriate section of the CRF.

In the event of a study related procedure or an intolerable AE or AE \geq CTCAE 4.03 Grade 3 ([Section 5.4.8.1](#)), patients may be counseled to interrupt dosing permanently or temporarily. Doses not taken in such instances do not count as planned dose administrations and do not constitute lack of compliance.

Patients must bring all containers of study medication and any remaining tablets as well as the patient diary card with them at each scheduled visit. Patients will be instructed to notify the study center personnel of missed doses. Dates of missed or held doses will be recorded on the CRF.

At each visit, patients will be issued a patient diary card, which contains clear instructions on how and when to take the study medication and to record the time and date of each dose.

Each patient will record on the patient diary card the number of tablets of study medication taken and the time of taking them daily. This diary card will be returned to the study center at each scheduled visit.

The recorded information is required to be entered into the eCRF by study center personnel.

